10.4.6 Baseline Descriptive Statistics

Nonapplicable.

10.4.7 Planned Interim Analyses

There is no planned Interim analysis.

10.4.8 Sub-Group Analyses

Subgroup analyses may be performed for surgical approach and type of the Gentrax Surgical Matrix used for cases of recurrence with reoperation post index procedure, if used.

10.4.9 Tabulation of Individual participant Data

All data collected in this study will be provided in subject data listings by study visit.

10.4.10 Sensitivity Analyses

All data will be analyzed as they were collected in the database. Missing data will not be imputed.

11 Regulatory, Ethical, Compliance and Operational Considerations

11.1 Informed Consent and Informed Consent Process

For this study, an IRB approved consent and consent process were used.

11.2 Protocol Amendment

Investigator may not modify (amend) this clinical investigation plan without obtaining written concurrence of the Sponsor, involved Ethics Committee(s), and applicable regulatory authorities.

11.3 Protocol Deviations

A Deviation is an Instance of failure to follow, intentionally or unintentionally, the requirements of the CIP. The investigator is not allowed a planned deviation from the CIP without first receiving approval in writing from the Sponsor.

Such deviations are documented on eCRFs and reported to the Sponsor as soon as possible.

1. LIST OF ABBREVIATIONS

Abbreviation	Term
AE	Adverse Event
ADE	Adverse Device Effect
CFR	Code of Federal Regulations
CSF	Cerebrospinal fluid
eCRF	Electronic Case Report Form
EMR	Electronic Medical Records
FDA	Food and Drug Administration
GCP	Good Clinical Practices
ICF	Informed Consent Form
ICH	International Conference on Harmonization
Integra	Integra LifeSciences Corporation
IRB	Institutional Review Board
LOS	Length of Hospital Stay
MedDRA	Medical Dictionary for Regulatory Activities
PMCF	Post Market Clinical Follow-up.
SADE	Serious Adverse Device Event
SAP	Statistical Analysis Plan
SAS	Statistical Analysis System
SD	Standard Deviation
SOA	Schedule of Activities
SOP	Standard Operating Procedures
SSI	Surgical Site Infection
SSO	Surgical Site Occurrence
SSOPI	Surgical Site Occurrences Requiring Procedural Intervention
USADE	Unanticipated Serious Adverse Device Event

2. INTRODUCTION

This document provides a detailed description of the statistical methods and procedures to be implemented during the analysis of the clinical study. The methods and procedures are intended to support the generation of study report, including detailed descriptions of the populations and methodologies, as well as summary tables, listings and graphics.

This statistical analysis plan (SAP) is based on Version 1.0 of the Protocol #T-GENVIH-003.

3. STUDY OBJECTIVES

The primary objective of this study is to collect additional safety data and demonstrate the performance of Integra GENTRIX® Surgical Matrix for reinforcement of ventral hernia repairs from a sub-population of participants in the T-GENVIH-002 study, specifically those with laparoscopic or robotic repair. Prospective data will be collected and assessed for later post-operative surgical site events and complications in the post-operative period from the last timepoint of data collection in T-GENVIH-002 to present. The safety objective of this study is to capture existing GENTRIX® Surgical Matrix Complication data in the longer term period post primary repair procedure, not previously reported in T-GENVIH-002 study. This study adds to the available data evaluating the safety and effectiveness of GENTRIX® Surgical Matrix in ventral hernia repair, particularly in a real-world population and particularly in the sub-population of minimally invasive surgery (MIS) cases (i.e., laparoscopic and robotic) from the GENVIH-002 study.

3.1 Primary Endpoint

The primary endpoint of this study is the incidence of clinically confirmed recurrence of the primary hernia to date, including not previously reported in T-GENVIH-002 study

3.2 Secondary Endpoint

1. Incidence of self-reported recurrence (i.e., bulge) of the primary hernia to date, including not previously reported in T-GENVIH-002 study.
2. Incidence of Surgical Site Occurrences requiring procedural intervention (SSOPI) of the primary hernia repair to date, not previously reported in T-GENVIH-002 study.
3. Incidence of Surgical Site Occurrences (SSOs) of the primary hernia repair to date (seroma, abscess, dehiscence, hematoma, wound necrosis, ileus, fistula, delayed wound healing), including not previously reported in T-GENVIH-002 study.
4. Incidence of Surgical Site Infections (SSIs) post primary hernia repair to date, including not previously reported in GENVIH-002 study.
5. Incidence of reoperation requirement of the primary hernia repair to date, including not previously reported in GENVIH-002 study.

3.3 Safety Endpoint

The safety endpoint of this study is the incidence of complication data in the later post-operative period to date, not previously reported in the T-GENVIH-002 study.

4. STUDY DESIGN

The Gentrix Ventral Hernia Repair study is a single-arm, prospective, single-center, post-market study.

5. STUDY PROCEDURE

This retrospective study specifically aims to collect data from the day of the primary hernia surgical repair procedure longer term post-operatively to date, including not previously reported in T-GENVIH-002 study. Data will be collected via a phone visit and questionnaire administered by the study coordinator (or, in the alternative, an in-office visit and questionnaire administered by the study coordinator) and entered into an electronic data capture system by the site. The following data will be collected on the Long Term Follow Up (LTFU) of the primary hernia repair.

The patients will provide informed consent to allow use of their data. There is no traditional enrollment period in this study. Data will begin to be collected from the first patient who meets all the eligibility criteria. The total expected duration of the study is approximately 3 months.

Table 1: Schedule of Data Collection Activities

	Screening	Subject Visit 1
*Prospective Data Collection		
Eligibility/Consent	X	
Complete Case Report Form(s)	X	X
¥Adverse Events	X	X

6. PROTOCOL DEVIATION

Protocol violations will be tracked by the study team throughout the conduct of the study. Data will be reviewed prior to closure of the database to ensure all important violations are captured and categorized.

A major protocol deviation is any significant protocol deviation that threatens the scientific validity of the data collection for a subject or is a serious violation of ethical study compliance and GCP. Examples of major protocol deviations include but are not limited to the following:

- Violation of inclusion/exclusion criteria at enrollment

7. ANALYSIS POPULATION

Enrolled: The enrolled population includes all eligible subjects based on the defined inclusion and exclusion criteria.

Intent-to-Treat (ITT) Population: All subjects who are enrolled into the study provide informed consent waiver and receive study intervention.

Per-Protocol (PP) Population: All subjects in the full Analysis Set not identified as major protocol violations.

The endpoints analysis will be based on the Intent-To-Treat population. The per-protocol set will be supportive and will be used to assess the robustness of study results if necessary. Safety analysis will be based on the Intent-To-Treat population.

8. SAMPLE SIZE DETERMINATION

Subjects from that consecutive series will be included in the study based on the defined inclusion and exclusion criteria, the subgroup of T-GENVIH-002 subjects underwent Laparoscopic or Robotic surgery. The sample size is not based on hypothesis testing. The planned sample size for this study will be approximately 21 treated subjects.

9. STATISTICAL ANALYSES

9.1 General Statistical Considerations

Descriptive statistics will be used to summarize study outcomes. No formal statistical testing will be performed. The study objectives will be presented by summary statistics.

For categorical data, frequencies and percentages will be provided. For continuous data, descriptive statistics, including sample size, mean, median, standard deviation, and range of values (i.e., minimum, and maximum values) will be provided.

A separate Table Listing Graphs (TLFs) will be provided.

All statistical analysis will be conducted using SAS® for Windows, version 9.4 or later.

9.2 Study Subjects

9.2.1 Disposition of Patients

The disposition of all subjects in the study will be provided for all available data. The numbers of subjects signed informed consent waiver, screen failed, enrolled, completed, and discontinued during the study will be summarized. Disposition and reason for study discontinuation will also be provided as a by-subject listing.

9.2.2 Demographics

Baseline demographics will be summarized and provided from T-GENVIH-002 study. By subject listings will be provided for each subject reported if necessary.

9.2.3 Medical History

The subject's relevant medical history will be summarized and provided from T-GENVIH-002 study. By subject listings will be provided for each subject reported if necessary.

9.2.4 Concomitant Medication

The subject's relevant medication history (i.e. medication taken up to prior to surgery) and relevant concomitant medication (i.e. current medication) will be summarized and presented by count and percentage of subjects as captured on the CRFs from T-GENVIH-002 and current study. Only immunomodulators and opioids are to be reported. By subject listings will be provided for each subject reported if necessary.

9.2.5 Surgery Evaluation

Not applicable.

9.2.6 Follow-Up Visit 1 Questionnaire

The Follow-Up Visits details will be summarized and presented by count and percentage of subjects as captured on the CRF. These information include but not limited to:

1. Incidence of Surgical Site Occurrences requiring procedural intervention (SSOPI) of the primary hernia repair to date, not previously reported in T-GENVIH-002 study.

2. Incidence of Surgical Site Occurrences (SSOs) of the primary hernia repair to date (seroma, abscess, dehiscence, hematoma, wound necrosis, ileus, fistula, delayed wound healing), including not previously reported in T-GENVIH-002 study.
3. Incidence of Surgical Site Infections (SSIs) post primary hernia repair to date, including not previously reported in GENVIH-002 study.
4. Incidence of clinically confirmed recurrence of the primary hernia occurred to date, including not previously reported in T-GENVIH-002 study.
5. Incidence of self-reported recurrence (i.e., bulge) of the primary hernia to date, including not previously reported in T-GENVIH-002 study.
6. Incidence of reoperation requirement of the primary hernia repair to date, including not previously reported in GENVIH-002 study.

By subject listings will be provided for each subject reported.

9.2.7 Study Exit

Study exit type will be summarized and presented by count and percentage of subjects as captured on the Study Exit CRFs. By subject listings will be provided for each subject reported.

9.2.8 Time to Hernia Recurrence Survival Analyses

Time to recurrence Kaplan-Meier Curve will be provided for all subjects with hernia recurrences at follow-up visits.

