9.3.1 Analysis of the Primary Endpoints

The incidence of clinically confirmed recurrence of the primary hernia occurred to date, including not previously reported in T-GENVIH-002 study will be summarized. The proportion of subjects with the incidents will be presented.

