11. MISSING DATA

Reasonable efforts will be made to obtain complete data for all subjects. Nevertheless, given the nature of this study (i.e. Retrospective), it is anticipated that missed visits/evaluations will occur and hence there will be missing data on some of the endpoints. Missing data will not be imputed.

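### The Kaplan-Meier curve for time to recurrence is limited to subjects who recurred, so it ends at 0% recurrence-free however well the device performs

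*SAP*

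**What the plan says.** SAP section 9.2.8 consists of one sentence: "Time to recurrence Kaplan-Meier Curve will be provided for all subjects with hernia recurrences at follow-up visits". It gives no time origin, no rule for dating a recurrence, no censoring rule and no numbers at risk. It also does not say which recurrence is the event. Section 9.2.6 lists both the clinically confirmed type and the self-reported type ("Incidence of self-reported recurrence (i.e., bulge) of the primary hernia to date, including not previously reported in T-GENVIH-002 study").

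Elsewhere, SAP section 7 states that "The endpoints analysis will be based on the Intent-To-Treat population", a population defined without regard to outcome. SAP section 9.3.1 analyses the primary endpoint, clinically confirmed recurrence, as a crude proportion: "The proportion of subjects with the incidents will be presented". On size, section 8 says "The planned sample size for this study will be approximately 21 treated subjects" and "The sample size is not based on hypothesis testing"; section 9.1 adds "No formal statistical testing will be performed". On incomplete data, section 11 says only "Missing data will not be imputed". The protocol (section 10.4) contains no time-to-event analysis, so nothing there fills the gap.

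**The concern.** A Kaplan-Meier curve estimates the probability of remaining event-free. It does so by counting, at each event time, everyone still under observation, including those who never have the event. Selecting subjects because they had the event removes exactly those people. The resulting curve describes when failures happened among the failures and cannot be read as a recurrence-free probability.

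This matters because longer-term recurrence is the study's main question and this is the only planned analysis that uses time. The primary proportion counts recurrences up to the interview. Follow-up runs from surgery to the present, no fixed length is set, and the study lasts about three months, so length of follow-up will vary with surgery date. The curve is the one analysis that could allow for that variation, and as worded it cannot. A reader who took a curve falling to zero at face value would badly underestimate the durability of the repair.

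**Working it through.** The plan states no figure that depends on this point: the sample size of about 21 has no assumed rate, precision or power behind it. The check is therefore on the estimator itself.

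**Formula.** S(t) = product over event times up to t of (1 − d/n), where d is the number of events and n the number at risk. If every subject in the set has the event and none is censored, then d = n at the last event time. That factor is 0, so S = 0.

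**Different recurrence counts.** N = 21 is from SAP section 8. The recurrence count r is assumed, as is follow-up of recurrence-free subjects beyond the last event. With all subjects included, the final value is then 1 − r/21.

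| r of 21 | Curve as written, final S | All 21 subjects, final S |
|---|---|---|
| 1 | 0% | 20/21 = 95.2% |
| 2 | 0% | 19/21 = 90.5% |
| 3 | 0% | 18/21 = 85.7% |
| 5 | 0% | 16/21 = 76.2% |
| 7 | 0% | 14/21 = 66.7% |
| 10 | 0% | 11/21 = 52.4% |
| 15 | 0% | 6/21 = 28.6% |

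The exact (Clopper-Pearson) 95% interval for the recurrence proportion is 1.2% to 30.4% at 2/21 and 25.7% to 70.2% at 10/21. These are very different results, yet the restricted curve ends at the same point for both. The restricted curve also always reaches a median time to recurrence; with all 21 subjects the median is not reached for any count tried up to 10. With r = 0 the restricted curve cannot be drawn, whereas the full-set curve stays at 100%.

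**Unequal follow-up.** In 2,000 simulated sets per count, censoring times were uniform from 30 to 60 months and event times uniform from 3 to 40 months (all assumed). With all subjects included, the median final S was 95.2% (r = 1), 90.5% (r = 2), 75.3% (r = 5) and 65.5% (r = 7). The recurrence-only curve ended at 0% in every set.

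**Worked illustration (assumed).** There are 3 recurrences, at 12, 24 and 36 months, and 18 recurrence-free subjects with censoring times evenly spaced from 30 to 60 months. The spacing is 30/17 = 1.76 months, so four are censored before month 36 (at 30.0, 31.8, 33.5 and 35.3). The number at risk at month 36 is 21 − 2 − 4 = 15.

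| Month | As written (at risk 3, 2, 1) | All subjects (at risk 21, 20, 15) | Gap |
|---|---|---|---|
| 12 | 2/3 = 66.7% | 20/21 = 95.2% | 28.6 points |
| 24 | 2/3 × 1/2 = 33.3% | 20/21 × 19/20 = 90.5% | 57.1 points |
| 36 | × 0/1 = 0% | × 14/15 = 84.4% | 84.4 points |

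**The case against.** The strongest reply is that the sentence is loose drafting for a curve on all subjects, with recurrence at follow-up as the event. The heading refers to survival analyses, Kaplan-Meier is named, and section 7 points to the Intent-to-Treat population. The SAP is loosely worded in other places too: section 4 calls the study prospective and section 5 calls it retrospective. That may well be what was meant, but it strains the grammar, nothing in either document says so, and a programmer following the text would drop the recurrence-free subjects.

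Second, zero is not strictly certain. If subjects entered on either type of recurrence but only clinically confirmed recurrence counted as the event, some would be censored and the curve could stop above zero. This is true, but it requires a mismatch that the SAP does not state, and the set would still be selected on outcome.

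Third, the curve is descriptive and sits outside the endpoint analysis in section 9.3. There is no formal testing, and the primary proportion and the by-subject listings will appear beside it. This stands and limits the damage: a reader would see 3/21, for instance, next to a curve ending at zero. It does not make the curve valid.

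Fourth, the size of the gap depends on assumed inputs and is largest at the last event. This also stands, which is why the gap is shown at all three times and the final values over a range of counts.

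**Conclusion.** The concern holds. On the plain wording of SAP section 9.2.8, the curve is conditioned on recurrence and ends at 0% for any non-zero number of recurrences, provided that the event is the same recurrence that brought subjects into the set. It cannot distinguish good long-term performance from poor, and it conflicts with the Intent-to-Treat rule in section 7. In the illustration the error grows from about 29 percentage points at 12 months to 84 at 36 months. Those sizes rest on assumed event and censoring times; the zero endpoint does not. The error is confined to this supportive analysis. The primary proportion is computed separately and does not change, although it makes no allowance for unequal follow-up.

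**What to change.** Replace SAP section 9.2.8 with a definition along these lines:

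- **Population:** all subjects in the Intent-to-Treat population (the protocol's Full Analysis Set).
- **Time and event:** time from index repair to first clinically confirmed recurrence, using the date of diagnosis and not the date of interview. Any curve for self-reported recurrence should be separate and labelled as such.
- **Censoring:** subjects without recurrence are censored at Visit 1, or at last known contact.
- **Dates from recall:** a stated rule for recurrence dates known only approximately from the interview.
- **Presentation:** numbers at risk, estimates with 95% confidence intervals at fixed times since repair, and the median and range of follow-up. The presentation items are not needed to correct the risk set, but with about 21 subjects they are needed to read the curve properly.

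The cost is mainly SAP wording, with no added visits or subjects. Two dates need confirming. The index surgery date should come from T-GENVIH-002, but SAP sections 9.2.2 to 9.2.4 bring over only demographics, medical history and medication, and section 9.2.5 marks surgery evaluation as not applicable. The recurrence date is not among the questionnaire items in Protocol section 6.1.2, although the adverse event form (Protocol section 7.3.1) records onset. If the case report form does not capture it, one field has to be added.

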9.2.9 Safety and Complications

All complications during the index surgery, discharge and follow-up visits including Device Deficiency and Adverse Event will be summarized. By subject listings will be provided for each subject reported.

9.3 Endpoint Analysis

Primary, Secondary and Safety Endpoints will be analyzed based on the Visit 1 Questionnaire report.

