Description of Sites/Facilities Enrolling Participants	One site located in the United States (US) will participate in this study.
Study Duration	Approximately three months.
Study Visits/Schedule of Study Activities	This prospective study specifically aims to collect data from the day of the primary hernia surgical repair procedure longer term post-operatively to date, including not previously reported in T-GENVIH-002 study.
Data Collection	Data will be collected via a phone visit and questionnaire administered by the study coordinator (or, in the alternative, an in-office visit and questionnaire administered by the study coordinator) and entered into an electronic data capture system by the site. The following data will be collected on the Long Term Follow Up (LTFU) of the primary hernia repair.

	Clinical Performance and Safety Evaluation: 
 1. SSOPI 2. SSO(s) 3. SSI(s) 4. Hernia Recurrence 5. Reoperation(s) 6. Adverse Event(s)
Statistical Methods & Analyses	
Study outcomes will be summarized using descriptive statistics. Categorical variables will be summarized using frequencies and percentages. Continuous variables will be summarized using means, standard deviations, medians, quartiles, ranges, and numbers of observations.
 
Statistical analysis will be based on data from all evaluable subjects meeting the eligibility criteria.

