3.1 Primary Objective

The primary objective of this study is to capture existing clinical performance data to confirm the continued performance of the Gentrix® Surgical Matrix as a long term follow up (LTFU) to T-GENVIH-002 study for minimally invasive surgical approach (laparoscopic and robotic) sub-population of cases post primary hernia surgical repair to date, not previously reported in the T-GENVIH-002 study.

Existing clinical data support the safety and performance of the Gentrix® Surgical Matrix. There are currently no safety concerns with these products. This clinical investigation will confirm the safety and performance of the Gentrix® Surgical Matrix particularly in MIS cases and identify any unknown or not previously reported side-effects.

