3.3 Primary Endpoint

The primary endpoint of this prospective study is to determine the incidence of clinically confirmed recurrence of the primary hernia to date, including not previously reported in T-GENVIH-002 study.

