6.1.2 Visit 1 Questionnaire

The patients' data to be collected from the last data collection of GENVIH-002 study to date, including not previously reported, are:

- Clinically confirmed recurrence of the primary hernia repair
- Self-reported recurrence (i.e., bulge) of the primary hernia
- Surgical Site Occurrences requiring Procedural Intervention (SSOPI)
- Surgical Site Occurrences (SSOs)
- Surgical Site Infections (SSIs)

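### Protocol 6.1.2 starts the Visit 1 recurrence data where T-GENVIH-002 ended, and SAP 9.3 bases the endpoints on that questionnaire, so recurrences already on record can drop out of a cumulative primary proportion

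*SAP*

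**What the plan says.** **Endpoint.** Protocol 3.3 defines the primary endpoint as the "incidence of clinically confirmed recurrence of the primary hernia to date, including not previously reported in T-GENVIH-002 study". SAP 3.1 agrees, and SAP 9.3.1 repeats it: "The incidence of clinically confirmed recurrence of the primary hernia occurred to date, including not previously reported in T-GENVIH-002 study will be summarized". SAP 9.3.1 adds that a proportion of subjects will be shown.

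**Window.** The synopsis (study visits row) states: "This prospective study specifically aims to collect data from the day of the primary hernia surgical repair procedure longer term post-operatively to date". SAP 5 has the same start point: "specifically aims to collect data from the day of the primary hernia surgical repair procedure longer term post-operatively to date". Protocol 4.1 also runs from the index procedure to the present. Protocol 6.1.2, which defines the Visit 1 Questionnaire and lists clinically confirmed recurrence first, has "data to be collected from the last data collection of GENVIH-002 study to date".

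**Source.** SAP 9.3 states: "Primary, Secondary and Safety Endpoints will be analyzed based on the Visit 1 Questionnaire report". The SAP names T-GENVIH-002 as a source for demographics (9.2.2), medical history (9.2.3) and medication (9.2.4). It does not name it for recurrence, surgical site events, infection or reoperation.

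**The concern.** A questionnaire that covers only the time after T-GENVIH-002 cannot, on its own, give a cumulative incidence since repair. The events it misses are those already known to the sponsor: recurrences recorded in T-GENVIH-002. The subjects concerned are still part of the analysis population, so they dilute the proportion.

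If the questionnaire instead covers the whole time since repair, as the synopsis and SAP 5 say, earlier recurrences enter only if the subject mentions them in the interview. Nothing says which source prevails when the subject's account and the T-GENVIH-002 record differ.

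The study has no hypothesis and no test (Protocol 10.1, SAP 9.1), so the reported proportion is itself the primary result. Two analysts who follow different sections could report different proportions from the same patients.

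**Working it through.** **Figure in the plan.** There is none to reproduce. The planned size of about 21 (Protocol 10.2, SAP 8) is the count of eligible subjects, and SAP 8 says that it does not rest on a hypothesis test.

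**Sections side by side, for recurrence**

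| Section | Start of data |
|---|---|
| Synopsis, study visits; SAP 5 | Day of repair |
| Protocol 4.1 | Index procedure |
| Protocol 6.1.2 | Last T-GENVIH-002 data collection |

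The synopsis study description and SAP 3 also use the later start ("in the post-operative period from the last timepoint of data collection in T-GENVIH-002 to present"), but for surgical site events and complications.

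**Inputs**
- n = 21 subjects, from the plan; n = 15 is an assumption, for incomplete contact.
- b = subjects who report a recurrence at Visit 1. Assumed b = 1, a new event.
- a = subjects with a recurrence on the T-GENVIH-002 record who report none at Visit 1. Not in the documents; taken as 0, 1 or 2.

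**Reading 1: Protocol 6.1.2 with SAP 9.3**

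Reported proportion = b/n. Cumulative proportion as the endpoint is worded = (a + b)/n. Understatement = a/n.
- a = 0: none.
- a = 1, n = 21: 1/21 = 4.8 points.
- a = 1, n = 15: 1/15 = 6.7 points.

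With b = 1 and n = 21 (exact 95% Clopper-Pearson intervals), the questionnaire alone gives 1/21 = 4.8% (0.1 to 23.8). The cumulative result is:
- a = 1: 2/21 = 9.5% (1.2 to 30.4)
- a = 2: 3/21 = 14.3% (3.0 to 36.3)

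The intervals overlap widely. The issue is which count is reported, not whether the two differ significantly.

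**Reading 2: day-of-repair window, recall only**

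Assume 1 new recurrence and 2 earlier ones, of which m are recalled. Reported proportion = (1 + m)/21, which is 4.8%, 9.5% or 14.3% for m = 0, 1 or 2. Only m = 2 gives the cumulative value.

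**Denominator for new recurrences**

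With 2 earlier recurrences (assumed) and 1 new one, all subjects give 1/21 = 4.8% (0.1 to 23.8). Subjects with no recurrence on the T-GENVIH-002 record give 1/(21 − 2) = 1/19 = 5.3% (0.1 to 26.0). The plan does not say which applies.

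**The case against.** The best defence is that the intent is plain. The endpoint wording, the synopsis, Protocol 4.1 and SAP 5 all point to repair-to-date, and Protocol 6.1.2 itself goes on to take in events not previously reported. That stands as evidence of intent, and it is why 6.1.2 is treated here as the outlier. It does not close the gap: at most it adds events that T-GENVIH-002 missed, not those it recorded.

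A second defence is that SAP 9.3 makes the questionnaire the basis of the analysis without excluding other sources. A reader might infer that the SAP forbids use of the T-GENVIH-002 outcomes; the text does not go that far. SAP 9.2.8 plans a time-to-recurrence curve, and SAP 9.2.9 covers complications at index surgery and discharge. Both imply earlier data, but neither states a source or a rule.

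Third, the eCRF, phone script and table shells are not in the documents and may settle part of this. Subject listings would also show the Visit 1 events behind the proportion. Both points are fair, but the SAP should carry the counting rule for its own primary endpoint.

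A reader might also infer that the error could equally be an overstatement, because Protocol 3.1 limits the primary objective to the "sub-population of cases post primary hernia surgical repair to date, not previously reported in the T-GENVIH-002 study". That would need the objective to override the endpoint statements in Protocol 3.3, SAP 3.1 and SAP 9.3.1. An objective to capture new data is compatible with an endpoint that reports all data, so that reading is not supported. Nor can one assume a complete earlier record for everyone: Protocol 10.4.2 speaks of patients who completed T-GENVIH-002, but the inclusion criterion in 5.1 asks only that they were subjects in it.

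**Conclusion.** The point holds for the primary endpoint. The questionnaire as defined in Protocol 6.1.2, used as SAP 9.3 directs, cannot deliver the cumulative incidence that the endpoint describes. The understatement is a/n: 4.8 points per affected subject at n = 21, and zero if no earlier recurrence goes unreported at Visit 1. The documents do not show that any subject is affected, so they do not support a statement that the reported rate will be too low. They show that the plan does not prevent it. The counts of new and earlier recurrences and n = 15 are assumptions; only n = 21 comes from the plan. The rule should be fixed before the analysis, since a choice made once the counts are known could be influenced by them.

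How a recurrence can be called clinically confirmed on the strength of an interview is a separate, secondary labelling point, and this conclusion does not depend on it.

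**What to change.** 1. Align Protocol 6.1.2 with the synopsis, Protocol 4.1 and SAP 5, so that the recurrence window is the day of repair to the present.
2. In SAP 9.3, for each endpoint worded cumulatively, count a subject once if the event is in the T-GENVIH-002 database (where it was collected there) or is reported at Visit 1, over all analysed subjects. List every disagreement between the two sources.
3. Report events not previously reported in T-GENVIH-002 separately, with the denominator stated. For recurrence, use subjects with no recurrence on the T-GENVIH-002 record.
4. Use one wording for surgical site occurrences requiring procedural intervention. Protocol 3.4, SAP 3.2 and SAP 9.2.6 limit the endpoint to events not previously reported; the synopsis and Protocol 10.1 and 10.4.4 make it cumulative.

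**Cost.** A SAP change, and a protocol amendment with the approvals in Protocol 11.2. A coded link between the two studies is also needed, because Protocol 6.1.1 gives each subject a new study number. SAP 9.2.2 to 9.2.4 imply such a link but do not state it, and the sponsor should check that consent covers its use for outcomes. The reported rate may be less favourable.
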